17.17 Safety Monitoring

A physician (MD or DO) who serves in the Site PI or Medical Clinician study role will review or provide consultation for each Adverse Event (AE) and Serious Adverse Event (SAE), as needed. These reviews will include an assessment of the possible relatedness of the event to the study intervention or other study procedures. The physician (MD or DO) who serves in the Site PI or Medical Clinician study role will also provide advice for decisions to exclude, refer, or withdraw participants as required. In addition, the Sponsor will assign a Medical Monitor to this protocol to independently review the safety data, present it to the DSMB for periodic review, and provide PIs a Safety Letter when necessary. The Medical Monitor will determine which safety events require expedited reporting to the Sponsor, NIDA, Indivior, the DSMB and regulatory authorities. This will include events that are serious, related and unexpected. The study staff will be trained to monitor for and report AEs and SAEs.

Each of the sites has established practices for managing medical and psychiatric emergencies, and the study staff will continue to utilize these procedures. Medical Clinicians at each site will be responsible for monitoring participants for possible clinical deterioration or other problems, and for implementing appropriate courses of action.

17.17.1 Data and Safety Monitoring Board (DSMB)

An independent CTN DSMB will examine accumulating data to assure protection of participants' safety while the study's scientific goals are being met. The CTN DSMB is responsible for conducting periodic reviews of accumulating safety and efficacy data. It will determine whether there is support for continuation of the trial, or evidence that study procedures should be changed, or if the trial should be halted, for reasons relating to the safety of the study participants, the efficacy of the treatment under study, or inadequate trial performance (e.g., poor recruitment).

17.17.2 Safety Monitor / Medical Monitor

The CCC Safety Monitor/Medical Monitor is responsible for reviewing all adverse events and serious adverse events reported. All SAEs will be reviewed within one business day of being reported in the eClinical. The Safety Monitor/Medical Monitor will also indicate concurrence or not with the details of the report provided by the site. Where further information is needed, the Safety Monitor/Medical Monitor will discuss the event with the site. Reviews of SAEs will be conducted in the Advantage eClinical data system and will be a part of the safety database. All AEs are reviewed on a regular basis to observe trends or unusual events.

The CCC Safety Monitor/Medical Monitor will summarize each SAE and will provide a report to the Lead Investigator, Sponsor, and NIDA. If the event meets the criteria for FDA-defined expedited reporting, the CCC safety team and regulatory team will work together to submit an expedited safety report to the FDA. A copy of the expedited report will be submitted to the DSMB through the DSC. A copy of the expedited report will be submitted to Indivior and all participating sites. Other safety reports will be generated and presented at the scheduled Data Safety Monitoring Board (DSMB) meetings.

17.17.3 Adverse Events (AEs)

Standard definitions for adverse events and serious adverse events, their identification, characterization regarding severity and relationship to therapy, and processing are described in Appendix A.

For the purpose of this study, all AEs will require reporting in the electronic data system.

Events that are temporally associated with SL-BUP use, but that are not recorded using either the Medication Side Effects form, or a different study-specific CRF (e.g., withdrawal on the COWS/SOWS, Buprenorphine-XR/Placebo Injection Site Evaluation), will be recorded as an AE.

Events related to the injection of the study medication are recorded on the Injection Site Examination form and will not be duplicate reported on an AE form, unless they meet the SAE definition.

Events related to withdrawal symptoms are captured on the COWS and SOWS forms and will not be duplicate reported on an AE form, unless the event meets the definition of an SAE. Withdrawal symptoms not captured by scheduled COWS and SOWS form should be reported as an AE. Any spontaneous reporting of withdrawal symptoms by the participant will be captured using the AE form in the following situations: withdrawal symptoms reported at visits without scheduled specific structured questionnaires (COWS and SOWS CRFs) and withdrawal symptoms not listed in the specific structured questionnaires (COWS and SOWS CRFs) reported at any visit.

Any of these events that meet the definition of an SAE are reported on the AE/SAE form set.

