10.8 Rules for Immediate Study Review

The following rules will automatically trigger a review by the DSMB to determine if any action should be taken to adjust conduct of the trial:

- Three or more participants experience severe adverse reactions.
- Four or more participants have four consecutive positive urine toxicology screens for opioid use, and have been reevaluated through any means as having moderate to severe opioid use disorder.
- One or more serious, unexpected and suspected adverse reaction (SUSAR).

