11.3.3 Medication Side Effects

At the visit after the participant receives sublingual buprenorphine (Week 1, 2nd Visit), participants will be asked to report any expected adverse reactions experienced after taking SL-BUP using the Medication Side Effects form. The self-administered form lists different expected adverse reactions, and participants will rate each possible reaction according to the severity of their perceived reaction. Events that are documented on the Study Medication Side Effect form will not be duplicate-reported as AEs unless one or more SAE criteria are met.

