11.3.4 Buprenorphine-XR/Placebo Injection Site Evaluation

Unblinded medical personnel will examine the injection site during the study visit following each subcutaneous injection. These examinations will usually occur at visits immediately following injections but should occur at the next attended visit if any of the aforementioned visits are missed. Additional monitoring may also be required. Participants will be asked to immediately report any injection site reactions to allow evaluation, monitoring, and possible referral, as needed. In the event an injection site reaction is reported by a participant or an abnormality is identified during an injection site evaluation, it will be captured on this form. All injection site reactions should be documented on the Buprenorphine-XR/Placebo Injection Site Evaluation form throughout study participation (from first injection through Week 16 Follow-up). If the abnormality results in a

Serious Adverse Event (SAE), the Adverse Event forms must also be completed. Well-developed precautionary procedures will be followed to avoid adverse events associated with injectable study medication administration. For example, abdominal area will be assessed during the physical exam at screening to assure that subcutaneous depot administration is feasible. Individuals whose abdominal area is unsuitable for subcutaneous depot injection will be excluded from the study.

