16.9 Safety Analysis

Treatment emergent adverse events (AEs), including treatment emergent serious adverse events (SAEs), will be summarized by presenting the number of events, number of participants experiencing AEs, and the severity and relatedness of adverse events by treatment arm. All adverse events will be coded using MedDRA® (The Medical Dictionary for Regulatory Activities). The number and proportion of participants experiencing each treatment emergent AE will be provided overall and by treatment arm. Treatment emergent adverse events will be summarized by System Organ Class (SOC) and Preferred Term (PT). If a participant experiences multiple episodes of an event, then the event is only counted once. Detailed listings of treatment emergent adverse events and non-treatment emergent events in the safety population by treatment arm will be provided and include severity, relationship to study medication(s), and action taken, as available. The criteria for an immediate study review by the DSMB will be monitored closely. These criteria are either (1) three or more participants experience severe adverse reactions; (2) four or more participants have four consecutive positive urine toxicology screens for opioid use,

and have been reevaluated through any means as having moderate to severe opioid use disorder; or (3) one or more SUSAR.

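### Non-serious injection-site reactions and sublingual-buprenorphine side effects are kept off the AE form, and Section 16 plans no summary of the two forms that hold them

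*Combined protocol and SAP*

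**What the plan says.** The protocol routes three kinds of non-serious event to dedicated forms.

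- **Injection-site reactions.** Section 11.3.4: "All injection site reactions should be documented on the Buprenorphine-XR/Placebo Injection Site Evaluation form throughout study participation", from the first injection to Week 16. Section 17.17.3 adds that injection-related events "will not be duplicate reported on an AE form, unless they meet the SAE definition".
- **SL-BUP side effects.** Under Section 11.3.3 the participant completes a Medication Side Effects form at the second Week 1 visit and rates each reaction. Events on it "will not be duplicate-reported as AEs unless one or more SAE criteria are met". Section 17.17.3 makes SL-BUP events an AE only if no study-specific form has recorded them.
- **Withdrawal.** Section 17.17.3 has these symptoms "captured on the COWS and SOWS forms and will not be duplicate reported on an AE form" unless serious. It then adds: "Withdrawal symptoms not captured by scheduled COWS and SOWS form should be reported as an AE".

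On analysis, Section 16.9 promises: "The number and proportion of participants experiencing each treatment emergent AE will be provided overall and by treatment arm". It also plans summaries by severity, relatedness, System Organ Class and Preferred Term. Section 16.6 item 8 plans chi-square tests on the number and severity of AEs. Neither names a source form, but Appendix A says that reportable AEs and SAEs are captured on the AE form.

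On monitoring, the first trigger for immediate DSMB review in Section 10.8 is "Three or more participants experience severe adverse reactions". Section 16.9 and Appendix B (24.2, part C) repeat it. None of the three says which forms are counted.

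**The concern.** Appendix A defines an AE broadly, as any untoward medical occurrence during the trial, related to study drug or not. A non-serious injection-site reaction meets that definition but is kept off the AE form. If the AE tables are built from that form, the reported number of participants with an AE will not match the protocol's own definition. An expected local effect of the study injection would then appear in no by-arm result.

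Injection-site reactions matter most here, because they arise after the arms have diverged. The SL-BUP form matters less for the comparison, because both arms take the same active induction (Section 6.1.1), but leaving it out still understates total drug-related events.

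Monitoring is affected too. Appendices A and B have the DSMB receive AE listings and SAE summaries or narratives, and Appendix A specifies physician review of severity and causality for reportable AEs. A severe but non-serious reaction held only on another form has no stated route into either.

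**Working it through.** The plan gives no figure to reproduce on this point. The check traces each event type from form to analysis, followed by simple counts.

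**1. From form to analysis (non-serious events)**

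| Event | Where recorded | On the AE form? | Planned by-arm analysis |
|---|---|---|---|
| Injection-site reaction | Injection-site form (11.3.4, 17.17.3) | No | None in Section 16 |
| SL-BUP side effect listed on its form | Medication Side Effects form (11.3.3) | No | None in Section 16 |
| Withdrawal captured on scheduled COWS/SOWS | COWS/SOWS (17.17.3) | No | Mixed model (16.6 item 2) |
| Withdrawal at other visits, or not on the scales | AE form (17.17.3) | Yes | 16.9 and 16.6 item 8 |
| Other systemic event after injection | AE form | Yes | 16.9 and 16.6 item 8 |

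Only the first two rows have neither an AE record nor an analysis of their own. All the diverted events reach the AE form if they meet SAE criteria.

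**2. Share of the expected reactions**

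Section 4.3 lists eight reactions occurring in more than 5% of BUP-Inj subjects. Two are local (injection-site pruritus and pain): 2/8 = 25%. The other six (headache, constipation, fatigue, raised liver enzymes, nausea, vomiting) have no general exemption from AE reporting after injection.

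**3. Number of participants**

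- 246 randomized 1:1 gives 246/2 = 123 per arm.
- At the 5% floor, 123 × 0.05 = 6.15, so more than about 6 BUP-Inj participants for each local reaction.
- At assumed rates of 10% and 20% (not in the documents), 123 × 0.10 = 12.3 and 123 × 0.20 = 24.6.
- At the floor, participants with either reaction number between 6.15 (complete overlap) and 2 × 6.15 = 12.3 (no overlap). Some will already be counted for another AE, so the effect on the any-AE count could be anything from 0 to about 12.

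No placebo rate is given, so no arm difference can be calculated.

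**4. How much withdrawal is diverted**

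There are 12 × 2 = 24 regular medication-phase visits. COWS and SOWS are scheduled in Weeks 1, 5, 9 and 12. With one or two regular visits in Week 1, that is 1 + 3 = 4 or 2 + 3 = 5 visits. At the other 20 or 19 visits, reported withdrawal goes on the AE form.

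**5. Severe is not the same as serious**

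In Appendix A, Grade 3 (severe) means marked limitation of activity, with hospitalization merely possible. Serious requires death, threat to life, actual hospitalization or another listed outcome. A reaction can therefore be Grade 3 without being serious, which is the case that the SAE exception does not cover.

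**The case against.** The strongest reply is that the documents never say the tables use the AE form alone. Section 17.17.3 can be read as a rule against entering the same event twice, Section 16.9 tabulates adverse events without naming a form, and Section 16.0 defers detail to a formal SAP that is not among the documents. This stands as a limit on certainty: the omission is inferred from Sections 17.17.3 and 16.9 read with Appendix A. The current text still plans no summary of either form.

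A reader might also infer several stronger things that the documents do not support.

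- **That the AE tables lose the most drug-related events.** Six of the eight listed reactions remain reportable as AEs.
- **That incidence is biased low mainly in the BUP-Inj arm.** Section 4.3 names injection-site reactions among the placebo risks too, and both arms take SL-BUP. A differential undercount is not shown.
- **That withdrawal goes unanalysed.** It has a by-arm model and reaches the AE form at most visits. What remains is uneven ascertainment: the same symptom is a scale item at one visit and an AE at another.
- **That the DSMB trigger will undercount.** Appendix A defines an adverse reaction by cause, whatever form holds it. The trigger text is silent on source and does not exclude these reactions.

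One objection concerns the remedy. The Side Effects form is solicited and self-rated, injection sites are examined by unblinded staff, and AE-form events get physician review. Coding and grading all three alike would mix unlike data. That is right, and the fix keeps them apart.

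**Conclusion.** The concern holds as a gap in planned analysis and in the specification of the trigger, not in data collection. As written, non-serious injection-site reactions and SL-BUP side effects recorded on their own form appear in no planned by-arm summary. The clearest loss is two of the eight expected reactions, each in more than about 6 of 123 BUP-Inj participants. That count assumes equal arms of 123 and that the 5% threshold in Section 4.3 applies to this population. The effect on overall AE incidence, and the size and direction of any arm difference, are unknown. Whether severe but non-serious reactions on these forms count toward the three-participant trigger is unstated.

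This should be corrected. It does not touch the primary analysis, sample size or power.

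**What to change.** In Section 16.9, and in the formal SAP:

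1. Add a by-arm summary of the Injection Site Evaluation form: number of participants, type of reaction and severity.
2. Add a separate by-arm summary of the Medication Side Effects form, labelled as solicited and with severity as rated by the participant.
3. Add a participant-level table by arm of any AE or injection-site reaction, counting an event whichever form holds it.
4. State that reactions on these forms which a study physician grades as severe and causally related count toward the Section 10.8 trigger and enter the DSMB listings. Use the same wording in Sections 10.8 and 16.9 and in Appendix B.
5. Footnote the AE tables to say that withdrawal captured at scheduled COWS/SOWS visits is not in the AE counts. No further withdrawal analysis is needed beyond the planned models.

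The forms are already collected. The cost is some extra tables and physician review of severity and causality for the events on them.

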17.17.4 Serious Adverse Events

For the purpose of this study, all SAEs will require reporting in the electronic data capture system. Reporting of AEs and SAEs is described in Appendix A. The study sites are responsible for reporting all AEs and SAEs to the IRB of record (and local IRB, as applicable) per IRB guidelines.

17.17.5 Known Potential Toxicities of Study Medication

Specific known potential toxicities of the study medication include risk of overdose. Buprenorphine, as Sublocade™ in this study, is a Schedule III controlled substance. An IND will be on file with the FDA to provide safety monitoring. The medication will be handled and administered using the required REMS procedures. All other clinical considerations regarding risk for use of this medication, such as possible drug interactions or hepatic impairment, have been integrated in the exclusion criteria and safety monitoring procedures utilized in this study.

Refer to the package insert for Sublocade™ for complete list of adverse reactions and toxicities.

18.0 DATA MANAGEMENT

18.1 Design and Development

This protocol will utilize a centralized Data and Statistics Center (DSC). The DSC will be responsible for development of the electronic case report forms (eCRFs), development and validation of the clinical study database, ensuring data integrity, and training site and participating node staff on applicable data management procedures. Advantage eClinical, a web-based distributed data entry system, will be implemented. This system will be developed to ensure that guidelines and regulations surrounding the use of computerized systems used in clinical trials are upheld. The remainder of this section provides an overview of the data management plan associated with this protocol.

18.2 Qualitative Data Management

Qualitative data will be collected and analyzed by the study investigators. The study investigators will be responsible for developing the qualitative interview guide, obtaining IRB approval, training staff, as well as the collection and analysis of qualitative data.

18.3 Site Responsibilities

The data management responsibilities of each individual site will be specified by the DSC and outlined in the Advantage eClinical User's Guide and CRF Manual.

18.4 Data Center Responsibilities

The DSC will 1) develop and apply data management procedures to ensure the collection of accurate and good-quality data, 2) provide final Case Report Forms (CRFs) and electronic CRFs (eCRFs) for the collection of all data required by the study, 3) develop data dictionaries for each eCRF that will comprehensively define each data element, 4) prepare instructions for use of Advantage eClinical and for completion of CRFs/eCRFs, 5) conduct ongoing data validation and cleaning activities on study data collected from all participating sites, and 6) perform data validation and cleaning activities prior to any interim analyses and prior to the final study database lock.

18.5 Data Collection and Entry

Data will be collected at the study sites on source documents and entered by the site into eCRFs in Advantage eClinical or will be collected via direct entry into the eCRF. In the event that Advantage eClinical is not available, the DSC will provide the sites with CRF paper source documents and completion instructions. Data entry into Advantage eClinical should be completed according to the instructions provided, project specific training and guidelines established by DSC. Data entry into eCRFs shall be performed by authorized individuals. The investigator is responsible for maintaining accurate, complete and up-to-date records, and for ensuring the completion of the eCRFs for each research participant. Selected eCRFs may also require the investigator's electronic signature. In some situations, data collected on source documents will

not be entered into Advantage eClinical, but when it is entered, it will follow the guidelines stated above.

18.6 Data Editing

Data will be entered into the DSC automated data acquisition and management system (Advantage eClinical). eCRFs will be monitored for completeness and accuracy throughout the study. Dynamic reports listing missing values and forms are available to sites at all times in Advantage eClinical. These reports will be monitored regularly by the DSC. In addition, the DSC will identify inconsistencies within eCRFs and between eCRFs and post data clarification requests or queries in Advantage eClinical on a scheduled basis. Sites will resolve data inconsistencies and errors and enter all corrections and changes into Advantage eClinical.

The CCC will conduct regular monitoring visits, during which audits comparing source documents to the data entered on the eCRF will be performed. Any discrepancies identified between the source document and the eCRF will be corrected by the site.

Trial progress and data status reports, which provide information on items such as recruitment, availability of primary outcome, treatment exposure, regulatory status, and data quality, will be generated daily and posted to a secure website. These reports are available to the site staff, the local node staff, the lead node, the coordinating centers, NIDA CCTN and the Sponsor to monitor study progress overall and at each individual participating site.

18.7 Data Transfer/Lock

Study participant research data, which is for purposes of statistical analysis and scientific reporting, will be transmitted to and stored at the DSC. This will not include the participant's contact or identifying information. Rather, individual participants and their research data will be identified by a unique study identification number. The study data entry and study management systems used by clinical sites and by DSC staff will be secured and password protected.

The DSC will conduct final data cleaning activities and "lock" the study database from further modification. The final raw analysis datasets will be transferred to the Lead Investigator, Sponsor or designee and to NIDA, as requested, for storage and archive. De-identified versions of these datasets will also be provided to the NIDA CCTN-designated party for storage and archiving. These datasets may be posted on the NIDA Data Share website.

